4.1 Hypothesis

Our central hypothesis is that nipple stimulation with an electronic breast pump to induce labor increases spontaneous vaginal delivery, shortens duration of labor induction, improves patient-reported pain scores during labor, improves patient satisfaction and sense of self agency with the birthing process, and improve scores on the postpartum depression scale. We also hypothesize that participants assigned to nipple stimulation therapy during labor will be more likely to use breastfeeding as the sole source of nutrition at hospital discharge, which will be associated with improved maternal perception of milk supply, less severe newborn weight loss, and sustained breastfeeding for the recommended 6 months. Secondly, we hypothesize that intrapartum nipple stimulation will not increase fetal or neonatal morbidity outcomes. Last, by examining cost of care and health-related quality of life, we hypothesize that performing nipple stimulation therapy during labor will be more cost-effective than the comparator after considering their overall impact on labor and delivery, breastfeeding, and early infant nutrition and care in the first 6 months.

We also hypothesize that nipple stimulation therapy invokes the wide cascade of events that promote labor to a greater extent than IV oxytocin alone. We hypothesize that oxytocin in the plasma of patients performing nipple stimulation will rise less than among subjects receiving IV oxytocin at the time when the subject is first contracting regularly. We hypothesize that other proteins associated with labor (including but not limited to IL6, IL1beta, plasminogen activator inhibitor 1, C reactive protein, ICOS ligand, and ERP29 will rise more in the circulation of subjects receiving nipple stimulation therapy compared with IV oxytocin. We hypothesize that urinary metabolites of prostaglandin E2 and F2alpha will be higher in subjects receiving nipple stimulation therapy. We hypothesize that, on a systematic level, plasma changes among subjects partaking in nipple stimulation will differ from subjects receiving IV oxytocin. We hypothesize that nipple stimulation therapy will have earlier secretory activation as measured by milk sodium and conductivity) in the early days postpartum, compared to individuals receiving IV oxytocin alone.

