Specimen collection will be conducted as described in the previously published methodology (38).

For patients in non-spontaneous labor, blood and urine will be collected at 1) prior to cervical ripening, 2) after cervical ripening, and 3) after 2 hours of treatment (IV oxytocin or nipple stimulation). This is a maximum of 3 blood samples per subject. For control patients in spontaneous labor, a blood and urine specimen will be obtained at enrollment. Blood may be drawn in several ways depending on what is clinically appropriate: (1) venipuncture; (2) IV catheter placed as part of standard of care (SOC); and/or (3) IV catheter placed for research purposes. The research IV may be placed in addition to the SOC IV and may be used instead of research venipuncture. That is, research venipuncture and research IV will not both occur at the same time (only one or the other).

Urine samples (amount variable by patient) will be collected mid-stream in a sterile screw-top container 1) prior to cervical ripening, 2) after cervical ripening, and 3) after 2 hours of treatment (IV oxytocin or nipple stimulation). If a patient has an indwelling foley catheter, urine from the tubing will be collected at the time of adequate contractions. If a patient is being intermittently catheterized for urine, a urine sample will be collected as able, but the patient will not undergo additional bladder catheterization for the purpose of this study.

Blood and urine samples may not be collected at one or more of the specified time points due to logistical issues (eg. patient enrolled after cervical ripening, labor floor acuity prevents nurse from drawing blood, patient delivers before time point, etc.) and/or clinical care taking precedence.

Proteomic profiling will be conducted by mass spectrometry at the Keck MS & Proteomics Resource. Prostaglandin measurements will be performed by an external core facility with expertise in prostaglandin mass spectrometry methods (Vanderbilt Eicosanoid Facility). microRNA profiling will be conducted via bulk RNA sequencing by the Yale Center for Genome Analysis/Keck Core.

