2) The sample size of 988 for the primary outcome will be sufficient to detect a 9.4% or 10.8% absolute difference in breastfeeding as the sole source of nutrition (BSSN) at the time of delivery hospitalization postpartum discharge with 80% power and 90% power, respectively (two-sided test, $\alpha=0.05$). This represents the difference between an expected BSSN rate of 47% in the setting of synthetic oxytocin infusion without nipple stimulation (average rate at the study sites based on institutional data) and 56.4% (with 80% power) or 57.8% (with 90% power) with nipple stimulation therapy.

3) Assuming a 15% attrition rate at 2 weeks postpartum (the time frame for our primary cost-effectiveness analysis in Aim 3), the sample size of 988 will have 90% power for detecting a standardized effect size of 0.22 for the between-group difference in cost and difference in quality adjusted life years (QALY) (two-sided test, $\alpha=0.05$). This is considered a small effect size based on conventional criteria, hence if we observe an even larger effect size, we should be sufficiently powered.

The sample size for this biospecimen trial is based on the primary comparison, specifically the difference in primary biomarkers from baseline to after 2 hours of treatment between patients performing nipple stimulation therapy and those receiving IV oxytocin. Sample size calculations are based on differences between non-laboring and laboring patients from prior reports (Table). Sample size was determined to achieve 80% power to detect a difference with a two-tailed alpha level of 0.05. The final sample size of 48 per exposure group is based on the largest sample size required (IL1beta). Therefore, there is more than adequate power for the remainder of the biomarkers of interest.

To detect a 10 mM difference in sodium concentration between the intrapartum nipple stimulation therapy group and the immediate synthetic oxytocin infusion group at 48 hours postpartum, with a standard deviation of 20 mM, 80% power, and a significance level of 0.05, a sample size of 32 participants per group is required. Accounting for an expected 30% dropout rate, we plan to recruit 46 participants per group.

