The primary comparison for Aim 1 is the difference in biomarker concentration or MS counts from baseline to 2 hours of treatment between patients performing nipple stimulation therapy and those receiving IV oxytocin. Secondary comparisons evaluate the change with labor induction versus spontaneous labor. This unadjusted between-group comparison of the within-group change will be based on a Student's t-test, with a supportive analysis using Analysis of Covariance (ANCOVA) where the baseline biomarker level will be a covariate in a mean response profile model (MRP), which allows for different variances and covariances across time. The primary exposure variable will be treatment group with either compound symmetry (CS) covariance or heterogenous compound symmetry covariance (HCS) to account for the within-patient correlation in biomarker values across the time points of data collection; and the choice between the two covariance matrices will be made using a likelihood ratio test (LRT)

as these are nested models. Results will be summarized as estimated means of fold change at adequate contractions for each group and the between-group mean differences, with surrounding 95% Confidence Intervals. By specifying the model as an MRP, we can also conduct any comparisons of means (within/between groups across time), by using linear contrasts and the multivariate Wald Test. In the adjusted analyses, we will include in the MRP as covariates the between-group differences identified in the between-group comparisons. In a sensitivity analysis, since we will know the timing of each measurement relative to the initiation of treatment, we will use the actual time (compare linear, polynomial or spline effect of time) instead of the categorical time point in a linear mixed effects model (LME) with a random intercept for each woman and a possible random slope for each woman (also tested using an LRT). All biomarkers listed in the Table will be analyzed in the same manner, as all will be treated as continuous variables. For the exploratory hypothesis using the time to active labor, we will use a joint modeling approach: time to active labor modeled jointly with the mean trajectory of change over time in biomarker values; this model will allow us to estimate the between-group differences in the time to active labor, as it is also influenced by the biomarker values within each group.

Data Analysis Plan for the Milk Biospecimen Sub-Study:

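### Time to active labor is compared between arms only through a joint model with post-randomisation biomarkers, and the plan does not say whether the total or the biomarker-conditional effect is meant

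*Protocol*

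**What the plan says.** Protocol 6.4.3.2, in the analysis plan for the biospecimen sub-study, states: "For the exploratory hypothesis using the time to active labor, we will use a joint modeling approach". The model is described as "time to active labor modeled jointly with the mean trajectory of change over time in biomarker values". Its purpose follows: "this model will allow us to estimate the between-group differences in the time to active labor", with the qualifier "as it is also influenced by the biomarker values within each group". The section gives no equation, no association structure and no statement of which coefficient or contrast will be reported.

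Three other places bear on this:

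- Section 6.3 schedules a blood and urine sample "after 2 hours of treatment (IV oxytocin or nipple stimulation", so part of the trajectory is measured after randomised treatment has begun.
- Section 4.1 expects the arms to differ on these biomarkers. It holds that "nipple stimulation therapy invokes the wide cascade of events that promote labor to a greater extent than IV oxytocin alone" and that "oxytocin in the plasma of patients performing nipple stimulation will rise less than among subjects receiving IV oxytocin".
- Section 6.4.3.1 plans Kaplan-Meier estimates, a log-rank test and an adjusted Cox model, but for labor length. Time to active labor is not named there.

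**The concern.** The stated target is a difference between randomised groups, and the stated route runs through variables that the treatment itself may change. By the protocol's own hypotheses, the biomarkers lie on the path from treatment to labor. If the event part of the model contains both arm and the biomarker trajectory, the arm term answers whether the arms differ among women with the same biomarker course. The randomised question is whether the arms differ at all.

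The two questions can have opposite answers. If stimulation speeds labor through the measured pathways, the arm term shrinks toward zero. If infusion raises a biomarker that predicts labor timing among women in the same arm but does not itself bring labor forward, the arm term can differ from zero when the arms do not differ in total. With neither quantity named in advance and no unconditional comparison beside the model, the same data could support either mechanistic conclusion.

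**Working it through.** The protocol gives no effect size, event count or power for time to active labor, so there is no stated figure to reproduce. The check is whether the arm term of a joint model equals the group difference, and under which link.

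**Inputs from the protocol.** Sub-study size (6.4.2): "The final sample size of 48 per exposure group is based on the largest sample size required (IL1beta"; the sizing is on a biomarker difference, not on time to active labor. Two-sided alpha is 0.05 (6.4.2) and allocation is 1:1 (6.1.2).

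**Assumed inputs.** The arm shifts the 2-hour biomarker by 1 between-patient SD. The log hazard ratio per biomarker unit is 0.70, 0.35 or 0. Each patient has two pre-treatment samples and one 2-hour sample.

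**Model.** Let A be the arm, b the patient's random effect, β the arm effect on the biomarker, α the association with the hazard and γ the arm coefficient.

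- Trajectory link: log hazard = baseline + γA + α(b + βA). Here γ is the direct effect, and the total effect is γ + αβ.
- Random-effects-only link: log hazard = baseline + γA + αb. Here γ is already the total effect, given b.

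True totals, with β = 1 throughout:

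1. Fully mediated: 0 + 0.70 × 1 = 0.70
2. Cancelling: −0.70 + 0.70 × 1 = 0
3. Half mediated: 0.35 + 0.35 × 1 = 0.70
4. Biomarker unrelated to timing: 0.70 + 0 × 1 = 0.70

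**Results.** Maximum-likelihood joint model with a Weibull hazard, 48 per arm, 400 simulated trials per case. Entries are mean log hazard ratio and rejection rate. The Monte Carlo standard error of a rate is at most √(0.25/400) = 2.5 points.

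| Case | Arm coefficient, trajectory link | Total derived from same model | Arm coefficient, random-effects-only link | Arm-only Weibull |
|---|---|---|---|---|
| 1 (total 0.70) | −0.02, 7% | 0.70, 88% | 0.70, 88% | 0.55, 74% |
| 2 (total 0) | −0.74, 79% | −0.02, 6% | −0.02, 6% | −0.02, 7% |
| 3 (total 0.70) | 0.34, 32% | 0.70, 90% | 0.70, 90% | 0.65, 88% |
| 4 (total 0.70) | 0.71, 83% | 0.70, 92% | 0.70, 92% | 0.70, 92% |

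The arm-only estimate in case 1 is 0.55, not 0.70, because a hazard ratio averaged over patients differs from one given the patient's random effect. Both describe the total effect, on different scales.

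**No causal role for the biomarker.** A separate Cox simulation (1,000 trials, 48 per arm) gave the arm no effect on event time and let an unmeasured factor drive both biomarker and timing. The arm coefficient given the biomarker averaged −0.51 and rejected in 54% of trials; the arm-only test rejected in 4%.

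**A smaller shift.** The oxytocin row of the sample-size table in 6.4.2 gives 24.25/40.8 = 0.59 SD, although its footnote ties the effect size to adequate contractions and not to 2 hours. In a simpler Cox check with one error-free biomarker, a within-arm log hazard ratio of 0.5 per SD and a direct effect of −0.59 × 0.5 = −0.295 (total zero), the conditional arm coefficient rejected in 24% of trials at 48 per arm.

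**The case against.** A reader might infer that the plan tests a direct effect and reports it as the group difference. The documents do not support that. Section 6.4.3.2 gives no equation and never says that the arm coefficient is the reported contrast. Its sentence is not false as it stands: the total can be derived from the trajectory-linked model, and under a random-effects-only link the arm coefficient is the total given the random effect. The derived total even rejected more often than the arm-only test in case 1 (88% against 74%). The qualifier about biomarker influence also shows that the authors meant to consider timing and biomarkers together, and in a mechanistic sub-study a conditional quantity may be wanted.

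Further, the hypothesis is labelled exploratory, and time to active labor is not among the outcomes listed in 5.2.2. Labor length is compared by arm without biomarker conditioning in 6.4.3.1, so the joint model would not be the trial's only evidence on labor speed. The association structure is a detail that a statistical analysis plan commonly settles. The simulated rates rest on assumed effects, and in the cancelling case a direct effect exists by construction; it misleads only if it is presented as the total.

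All of this stands, and it keeps the severity low. It does not remove the point. The protocol itself pairs a target with a single route. References to the mean trajectory and to the influence of biomarker values point toward the trajectory link. Labor length is a different endpoint, so the unconditional comparison in 6.4.3.1 does not cover this one.

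**Conclusion.** The point holds in conditional form. The protocol relies solely on a joint model with a post-randomisation biomarker trajectory for the arm difference in time to active labor, and it fixes neither the target nor the link. Under the link that the wording suggests, the arm coefficient is biomarker-conditional. Presented as the group difference, it could miss a real effect (7% rejection against 74% for the arm-only test) or show one when the total is nil (79% against 7%).

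The mechanism follows from the model's form. The size depends on the assumed shift and biomarker-to-labor strength, and falls to 24% in the cancelling scenario with the smaller shift. There is no such distortion when the biomarkers are unrelated to labor timing, when only random effects are shared, or when the total effect is derived. Severity is low: the primary outcome and the sub-study's primary comparison of biomarker change are untouched.

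**What to change.** In 6.4.3.2, state that the arm difference in time to active labor is the total effect by randomised arm. Estimate it by a log-rank test and a Cox model containing only arm and the randomisation strata. The plasma and urine sub-study runs at Yale only, so site is constant and membrane status is the stratum that matters. Alternatively, name the total effect derived from the joint model, γ + αβ under the trajectory link. Choose one of the two in advance, because their hazard ratios are on different scales.

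Keep the joint model for the association between biomarkers and labor timing. State its link, and label its arm coefficient under the trajectory link as biomarker-conditional and exploratory.

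The cost is a few sentences and one simple model on data already to be collected. Nothing of the mechanistic analysis is lost.

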Because, in our preliminary studies, we have found less rise in maternal oxytocin among patients undergoing nipple stimulation, it is possible that other pathways are being activated in these patients. We intend to explore those other pathways using “omics” approaches to look at plasma proteins and microRNAs and urine prostaglandin metabolites. These studies have the potential to identify the mechanism(s) by which nipple stimulation induces labor, may point to differences with IV oxytocin that lead to the increased morbidities associated with prolonged and failed induction of labor, and may elucidate novel pathways involved in the stimulation of labor, which would contribute to our understanding of induction of labor. In order to understand the mechanisms by which nipple stimulation therapy induces labor, we will also compare the measurements of these biological variables in subjects prior to induction of labor and in control patients in early spontaneous labor.

Lastly, lactation is activated and triggered when a very tightly regulated cascade of events occurs at the end of the pregnancy and during labor, but may be negatively impacted by obstetric interventions. Secretory activation of the mammary gland initiates mature milk production in epithelial cells (usually occur 48-72h postpartum) and then milk ejection is triggered by oxytocin hormone and nipple stimulation (e.g., infant suckling or breast pump). Factors such as nulliparity, labor induction, and cesarean delivery have been shown to increase the risk of early lactation difficulties. Delayed secretory activation is a key predictor of suboptimal breastfeeding outcomes. It is biologically plausible that with IV oxytocin the normal secretory activation process for lactation is altered. Using milk biomarkers, we will examine the effect of nipple stimulation induced labor on lactation initiation in the first 48-72 hours after birth.

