Among the women enrolled in the translational sub-study at Yale, the following secondary outcomes will be explored:

- Plasma proteomic profiles (measured by mass spectrometry) after 2 hours of treatment comparing patients receiving IV oxytocin and nipple stimulation. Plasma samples from patients who have not undergone cervical ripening will be collected as additional control to account for differences achieved from cervical ripening alone. Plasma samples from patients in early spontaneous labor will be obtained to compare how closely nipple stimulation therapy and IV oxytocin approximate the molecular phenotype of spontaneous labor.
- Changes in plasma proteomic profiles from baseline (prior to treatment), 2 hours, and the time of adequate contractions in each treatment group
- Plasma micro-RNA profiles (measured by bulk RNA sequencing) after 2 hours of treatment among patients receiving IV oxytocin, nipple stimulation, and patients in early spontaneous labor.
- Changes in plasma micro-RNA profiles from baseline (prior to treatment), 2 hours, and the time of adequate contractions in each treatment group
- Urine prostaglandin profiles (measured by mass spectrometry) at 2 hours comparing patients receiving IV oxytocin, nipple stimulation, nipple stimulation who cross-over to IV oxytocin, un-ripened control patients, and patients in spontaneous labor.
- Changes in urine prostaglandin profiles from baseline (prior to treatment), 2 hours, and the time of adequate contractions in each treatment group

Among the women enrolled in the translational sub-study for milk collection, the following secondary outcomes will be explored:

- Changes in milk sodium and conductivity levels from before delivery (in the nipple stimulation therapy group only), and 12, 24, 48 hours after delivery. For mothers hospitalized for a longer period, additional samples at 72 hours will be collected or later up to twice a day.
- Milk macronutrient composition at 48 hours after delivery in each treatment group.
- Milk RNA profile at 48 hours after delivery in each treatment group.

The following secondary neonatal outcomes will be explored:

- Intrapartum fetal death or neonatal death (assessed until birth hospitalization discharge or death)
- Neonatal Apgar score ≤ 3 at 5 minutes of life
- Umbilical cord arterial pH < 7.0 or base excess > 12 mmol/L; or umbilical cord venous pH < 7.0 or base excess > 12 mmol/L if arterial blood sample not available

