Milk samples will be collected up to twice a day. Antepartum milk samples (10 drops to up to ½ teaspoon) will be collected from individuals in the nipple stimulation group during the intrapartum phase. Samples will be collected every 12 hours until labor. Volume will be determined by the mothers based on the amount of milk produced and how much they want to use to feed the infant postpartum.

Postpartum milk samples will be collected from IV oxytocin and nipple stimulation treatments participants at approximately 12, 24, and 48 hours postpartum. At 12, 24 and 72 hours 6-10 drops of milk (or more if participant allows) will be collected to a sterile tube using a pump or manually expressed from the breast. At ~48 hours postpartum, we will aim to collect 0.5-2.5ml of milk to perform all the sodium and milk conductivity assays mentioned below. If mothers are still hospitalized at 72 hours, additional samples will be collected every 12 hours up to twice per day (6-10 drops).

0.5ml of milk is needed for analysis of Sodium and milk conductivity, 0.5ml of milk for RNA analysis and 1ml of milk for macronutrients analysis.

Biological samples will be collected and stored at Yale and Weill Cornell Medicine (WCM) under secure, temperature-controlled conditions before shipment to [name] lab in Ithaca. At collection time, all samples will be de-identified and labeled with unique study ID numbers and time since delivery, which contain no personally identifiable information. Yale and WCM sites will use REDCap to code and manage the associated clinical data and sample collection records. A secure, access-restricted linkage key connecting study IDs to patient identifiers will be maintained solely by the local research teams. [name] lab will only receive de-identified samples and coded data labeled with the study ID, and will have no access to patient identifiers. Results generated by [name] lab will be uploaded to the WCM REDCap database using the matched study IDs provided with the samples, ensuring

all data remain de-identified and participant confidentiality is maintained throughout the study.

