The primary comparison will be looking at milk composition before and after birth for participants in the nipple stimulation group. We will use Student's t-test to compare the paired milk samples from the same individuals.

Secondary comparison will be looking into milk composition between patients performing nipple stimulation therapy and those receiving IV oxytocin versus spontaneous labor at 12, 24, 48 and 72 hours postpartum. We will account for multiple measurements for each participant (if multiple samples will be collected) and those will be used for a mixed effect model. Structural equation model will be used for modeling the effect of additional variables (delivery mode, intentions to breastfeed, feeding frequency, maternal intention to feed etc.) on milk biomarkers and breastfeeding outcomes.

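### The milk sub-study's primary comparison is before versus after birth in the stimulation arm alone, so it cannot separate a stimulation effect from normal milk maturation or test the between-arm hypothesis the sub-study was sized for.

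*Protocol*

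**What the plan says.** The milk paragraph of Protocol section 6.4.3.2 states: "The primary comparison will be looking at milk composition before and after birth for participants in the nipple stimulation group". The method follows: "We will use Student's t-test to compare the paired milk samples from the same individuals". The comparison of the randomised arms comes second: "Secondary comparison will be looking into milk composition between patients performing nipple stimulation therapy and those receiving IV oxytocin". It covers 12, 24, 48 and 72 hours postpartum, with a mixed model for repeated samples.

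Other sections set a different question:

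- Section 4.1 is comparative: "We hypothesize that nipple stimulation therapy will have earlier secretory activation as measured by milk sodium and conductivity", set against women receiving IV oxytocin alone.
- Sections 5.3.1 and 6.4.2 size the sub-study on a 10 mM sodium difference between the two arms at 48 hours, with SD 20 mM, 80% power and alpha 0.05. They give 32 per group, or 46 after 30% dropout.
- Section 3.2 places the normal onset of mature milk production at about 48 to 72 hours after birth.
- In section 6.3, antepartum milk samples "will be collected from individuals in the nipple stimulation group during the intrapartum phase"; section 5.2.2 likewise limits pre-delivery samples to that arm.
- Objective 7 in section 4.3 presents the before/after comparison as a way of seeing how milk changes. It lists the between-arm comparison beside it, without ranking the two.

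**The concern.** The comparison labelled primary uses no data from the control arm. Milk is expected to change across birth as part of ordinary secretory activation, and the protocol uses sodium and conductivity as markers of that process. A before/after difference in stimulated women is therefore what one would expect if stimulation did nothing to lactation. Because no pre-birth control milk exists, there is no control-arm change to subtract.

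The result ranked first would thus neither support nor refute the section 4.1 hypothesis, and the comparison that could do so is ranked second. The plasma and urine plan in the same section takes the opposite course: its primary comparison is the change from baseline contrasted between the arms. No reason is given for the difference.

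**Working it through.** **1. The plan's own figure.** Inputs from section 6.4.2: difference 10 mM, SD 20 mM, power 80%, alpha 0.05, two-sided (that section says all its estimates are two-tailed).

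- Two-group formula: n = 2·SD²·(1.960 + 0.842)²/difference² = 2·400·7.849/100 = 62.8, so 63 per group (64 by the t distribution).
- One-sample or paired formula: n = 400·7.849/100 = 31.4, so 32 (34 by the t distribution).
- Dropout: 32/(1 − 0.30) = 45.7, so 46.

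The stated 32 is not reproduced as the between-group size that the text describes. It matches only a one-sample or paired formula with 20 mM as the SD of the difference. The step from 32 to 46 is correct.

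**2. How often the primary test rejects when stimulation has no effect.** Assume 32 complete pairs, a two-sided 0.05 test and a normal maturation shift m. Power comes from the non-central t distribution with 31 degrees of freedom and non-centrality √32·m/s, where s is the SD of the within-woman change. If each sample has SD 20 mM and the within-woman correlation is r, then s = 20·√(2(1 − r)). This gives 20 mM at r = 0.5 and 28.3 mM at r = 0. The protocol states neither m nor r, so both are ranges.

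| Assumed shift m | s = 20 mM | s = 28.3 mM |
|---|---|---|
| 5 mM | 28% | 16% |
| 10 mM | 78% | 49% |
| 15 mM | 98% | 83% |
| 20 mM | >99.9% | 97% |

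A simulation of 20,000 trials, with the same shift in both arms and r = 0.5, agrees. The paired test rejected in 78% of trials at 10 mM and 99.98% at 20 mM. The between-arm test stayed at about 5% throughout.

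**3. What the between-arm comparison can deliver at the planned size.** With 32 evaluable per group, the standard error of the difference is 20·√(2/32) = 5 mM.

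- Power for 10 mM: Φ(10/5 − 1.960) = Φ(0.04) = 52%, or 50% by the t distribution.
- Difference detectable with 80% power: 5·2.802 = 14.0 mM.
- If all 46 per group were evaluable, power would be 67% (66% by the t distribution).
- For 80% power at 10 mM: 64 evaluable per group, or 64/0.70 = 91.4, so 92 recruited.

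**The case against.** The best defence is objective 7. If the before/after comparison is there to see how milk changes, a paired test answers it. The between-arm comparison is planned as well, at several time points, and the milk measures are secondary outcomes to be explored. The protocol attaches no decision rule or claim of benefit to the paired test. The sub-study plans 92 recruits (46 per group) within a trial of 988, and the trial's primary outcome is untouched. All of this stands and limits the weight of the point. It does not remove the mismatch: a descriptive aim is no reason to call a test primary when the hypothesis and the sizing are between arms.

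A reader might go further and infer that normal maturation is bound to make the primary test significant. The documents do not support that:

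- They give no size for the shift. At 5 mM the rejection rate is only 16% to 28%.
- Section 6.4.3.2 speaks of milk composition and fixes neither the analyte nor the postpartum time point for the pairing. A sample at 12 or 24 hours could precede most of the change that section 3.2 places at 48 to 72 hours.
- The number of complete pairs is uncertain, because the volume of intrapartum milk depends on what the mother produces and is willing to give.

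Nor does the protocol say that a before/after change will be reported as evidence that stimulation advances lactation.

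**Conclusion.** The point holds as an internal mismatch with a real inferential cost. The comparison named primary cannot distinguish a stimulation effect from normal maturation, and it does not test the hypothesis or match the stated sizing. That conclusion needs no assumed figure, since it follows from the one-arm design and the absence of pre-birth control milk.

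The rejection rates in the absence of a treatment effect (28% to over 99.9%, or 16% to 97%) are illustrations. They rest on the assumed shifts, on sodium as the analyte, on 32 complete pairs, and on an SD of change of 20 or 28.3 mM. Near-certain significance requires a shift of roughly 15 to 20 mM or more, which the protocol does not establish.

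Correcting the ranking exposes the sizing error, so the two belong together: the between-arm comparison has about 50% power on the stated inputs, not 80%. The matter is worth correcting, but it is confined to the sub-study.

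**What to change.** In the milk paragraph of section 6.4.3.2, name the between-arm difference in milk sodium at 48 hours, by randomised arm and estimated within the planned mixed model, as the primary comparison. Report the before/after comparison in the stimulation arm as descriptive (means with confidence intervals, no inference about the intervention), in keeping with objective 7.

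At the same time, restate the power in sections 5.3.1 and 6.4.2. With 10 mM, SD 20 mM and two-sided 0.05, 32 evaluable per group gives about 50% power, or 80% power for about 14 mM. Reaching 80% for 10 mM would take about 64 evaluable per group.

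While the paragraph is open, resolve its mention of spontaneous labor as a comparator, since section 6.3 plans milk collection only from the two randomised groups.

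The cost is a protocol amendment. Postpartum samples at 48 hours are already planned in both arms, so no new samples are needed unless the team chooses to enlarge the sub-study. The downside is that the primary milk result is less likely to be significant and the stated power looks less favourable.
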